CD62L	L-selectin
CD69	Early T-cell Activation Antigen 1
CD103	Integrin Alpha E
CD107	Lysosome-associated Membrane Proteins (LAMP)-1 and LAMP-2
CFR	Code of Federal Regulations
CICERO	Comprehensive Institutional Collaborative Evaluation of Research Online
CMI	Cell-mediated Immunity
CRF	Case Report Form
CTCAE	Common Terminology Criteria for Adverse Events

CTL	Cytotoxic T Lymphocyte activity
CVD	Center for Vaccine Development
CVD 103-HgR	The strain designation of live oral cholera vaccine, Vaxchora
DHHS	Department of Health and Human Services
DMEM	Dulbecco's Modified Eagle's Medium
DNA	Deoxyribonucleic Acid
EBV	Epstein-Barr virus
e.g.	For Example
EU	European Union
FDA	Food and Drug Administration, DHHS
FOXP3	Forkhead Box P3
FWA	Federalwide Assurance
GAPDH	Glyceraldehyde 3-phosphate dehydrogenase
GCP	Good Clinical Practice
GI	Gastrointestinal
HIV	Human Immunodeficiency Virus
HLA-DR	Human Leukocyte Antigen DR
HRPO	Human Research Protections Office
ICF	Informed Consent Form
ICH	International Conference on Harmonisation
IFN- γ	Interferon- γ
IgA	Immunoglobulin A
IgG	Immunoglobulin G
IL	Interleukin
IPC	Internal Position Control
IRB	Institutional Review Board
ISM	Independent Safety Monitor
IV	Intravenous
LCL	Lymphoblastoid Cell Lines
MHC	Major Histocompatibility Complex
MI	Milliliter

MOP	Manual of Procedures
mRNA	Messenger Ribonucleic Acid
NIAID	National Institute of Allergy and Infectious Diseases, NIH, DHHS
NIH	National Institutes of Health, DHHS
OCT	Optimal Cutting Temperature
OHRP	Office for Human Research Protections, DHHS
PBMC	Peripheral Blood Mononuclear Cells
PCR	Polymerase Chain Reaction
PI	Principal Investigator
PWM	Pokeweed Mitogen
QA	Quality Assurance
QC	Quality Control
QMP	Quality Management Plan
RPMI	Roswell Park Memorial Institute medium
rRNA	Ribosomal Ribonucleic Acid
SAC	Staphylococcus aureus Cowan
SAE	Serious Adverse Event
SEB	Staphylococcal enterotoxin B
SMC	Safety Monitoring Committee
SOP	Standard Operating Procedure
TCR	T-cell Receptor
TM	Memory T cells
TEM	Effector Memory T cells
TCM	Central Memory T cells
TEMRA	CD45RA+ Effector Memory T cells
TNF	Tumor Necrosis Factor
Tregs	Regulatory T Cells
UMB	University of Maryland Baltimore
US	United States
WHO	World Health Organization
Yrs	Years

Protocol Summary

Title: Collection of Blood for In Vitro Studies from Healthy Adults Who Have Received Oral Cholera Vaccine (CVD 103-HgR)

Protocol No.: Blood Donor CVD 9000

No.:

Phase: Specimen and data collection study

Population: Total of 200 healthy adults (ages 18 years or older) from the Baltimore-Washington metropolitan area and from the UMB campus

Number of 1

Sites:

Study indefinite

Duration:

Volunteer Up to 8 years

Participation

Duration:

Agent or Intervention: Licensed CVD 103-HgR oral *V. cholerae* O1 vaccine (Vaxchora®, PaxVax Inc., Redwood City, CA, USA)

Objectives:

1. To measure systemic and mucosal immune responses following immunization with the oral licensed cholera vaccine in consenting volunteers
2. To measure epigenetic changes which occur in response to vaccination with oral cholera vaccines
3. To integrate these multifaceted datasets into a systems biology approach to the understanding of the response to vaccination

Key Roles

Clinical PI [name], PhD
Assistant Professor of Pediatrics
Center for Vaccine Development
University of Maryland School of Medicine
[name]
[name]
Office [contact]
[contact]

Study Coordinator [name], CRNP
Center for Vaccine Development
University of Maryland School of Medicine
[name]
[name]
Office [contact]
[contact]

1 BACKGROUND INFORMATION AND SCIENTIFIC RATIONALE

1.1 Background Information

Vibrio cholerae, the causative agent of cholera, has the ability to cause a rapidly dehydrating diarrheal disease and is also a public health problem of developing countries, travelers, and deployed military personnel to areas lacking safe water and sanitation. A live oral cholera vaccine CVD 103-HgR has been licensed and a single oral dose demonstrated an efficacy of 80-90%.¹ Vaccination with CVD 103-HgR appears to confer sterilizing immunity in the gut.

Despite the availability of such an efficacious vaccine, the development of new and improved vaccines is severely hampered by a lack of information concerning the “true” (i.e., operative) immunological mechanisms underlying the protection elicited by cholera, which does not invade the mucosal surface. Specimens obtained from volunteers participating in this clinical study will be used to identify the immunological mechanisms of protection from *V. cholerae*. These mechanisms may be broadly applied to other enteric pathogens for which vaccines are not yet available.

1.2 Scientific Rationale

Immunological responses to *V. cholerae*

The immunological responses that correlate with protection from *V. cholerae* remain largely undefined or poorly defined. Thus, in depth studies of immune responses will be conducted with specimens from young adults and the elderly immunized with a single dose of CVD 103-HgR in this clinical research study. These studies should provide key insights into the characteristics and longevity of the immune responses that best correlate with protection from infection with *V. cholerae* and contribute to further our knowledge of the mechanisms underlying immunosenescence. Furthermore, these studies will enable a direct comparison of the magnitude and characteristics of the systemic and gut mucosa immune responses elicited by CVD 103-HgR immunization.

Summary

The specimens obtained in this clinical research study will be used to further our understanding of the protective immunological mechanisms that can be elicited systemically and may be applicable to other enteric pathogens.

2 STUDY OBJECTIVES AND OUTCOME MEASURES

2.1 Objectives

1. To measure the systemic immune response following immunization with oral licensed cholera vaccine in consenting volunteers
2. To measure epigenetic change which occur in response to vaccination with oral cholera vaccine
3. To integrate these multifaceted datasets into a systems biology approach to the understanding of the response to vaccination

2.2 Outcome Measures

2.2.1 Primary outcome

Percentage of responders by four-fold increase in vibriocidal antibody titers between pre- and post-immunization time-points.

2.2.2 Exploratory outcomes

The following brief descriptions provide some overview of the intended laboratory analyses to be performed with the specimens to be collected in this study. *This is not meant to be an exhaustive list of all the possible laboratory studies to be performed.*

1. Functional analysis of systemic (e.g., using serum, PBMC) anti-*V. cholerae* immune responses. These studies will include the following measurements, depending on specimen availability:
 - a. Ab levels to *V. cholerae* antigens in bodily fluids (e.g., serum, plasma)
 - b. Ab-secreting cells (ASC) to *V. cholerae* antigens
 - c. Cytokine production (e.g., intracellular IFN- γ , TNF- α , etc. by multichromatic flow cytometry or mass cytometry, IFN- γ production by Elispot and/or cytokine production in culture supernatants by multiplex technology.)
 - d. Memory (T_M) and B_M responses
 - e. CTL
 - f. innate immune responses (macrophages and dendritic cells)
2. Evaluation of homing characteristics of the various *V. cholerae*-responsive CD4+ and CD8+ T cell subsets
6. Study of TCR $\gamma\delta$ T cells and T_{reg} using multichromatic flow cytometry or mass cytometry using monoclonal antibodies to molecules that are characteristic of these cells (e.g., CD25 and FOXP3)
7. Measure the expression of host response genes to vaccination using functional genomics,

proteomics, and epigenetics

3 STUDY DESIGN

This study is a single center, open label clinical research study to study the effect of oral immunization with the CVD 103-HgR cholera vaccine in younger adults and older adults (i.e., elderly). Healthy adults, ages 18 years to 64 years, will be recruited from the Baltimore-Washington area in response to campus flyers, advertising, and word-of-mouth. Study participants will receive the cholera vaccine. Subsequent to vaccination, small volume (up to 200 mL) or large volume (200 mL or greater) blood draws will be requested; the timing of these blood draws are not strictly set and the schedules in *Appendix D* and *E* are provided to give a general overview of the flow of research procedures. The timing of the blood draws and the types (small or large volume blood) is dependent on the research laboratory's needs. In general, more frequent scheduled blood draws will occur in the first year after vaccination and less often in the years after vaccination (up to 8 years of planned follow-up). Therefore, we intend to regularly re-screen for anemia and have set limits on the total volume of blood to be collected over any 56 day period.

3.1 Screening

After informed consent has been completed, a medical history, concomitant medications, and vital signs are collected. Initial screening labs for eligibility include:

- Complete blood count (CBC) with differential, to assess total white blood count (WBC), hemoglobin, and platelet count
- Liver function tests to assess alanine aminotransferase (ALT) and aspartate aminotransferase (AST)
- Serologies for HIV
- Blood typing (this is not an eligibility criterion, but is used to guide the immunological analysis)

3.2 Interventions

Administration of licensed Live Oral Cholera Vaccine CVD 103-HgR. Participants will be given the vaccine, as packaged, and are to administer the vaccine as per the package insert. Briefly, approximately 100 mL of cool or room temperature purified bottled water is to be placed into a clean disposable cup. The contents of the buffer sachet are to be placed into the water and stirred. Then the contents of the active (lyophilized vaccine) sachet are to be placed into the water, then stirred for ~30 seconds. The reconstituted mixture should be completely ingested within 15 minutes. Illustrated instructions for the administration of CVD 103-HgR is presented in *Appendix E*.

Serial Blood Donor (small volume). After volunteers have been recruited, they may be contacted to have blood drawn, 1-20 times a year. No more than 2 $\frac{1}{3}$ cups (550 ml) will be taken over a 2-month period of time. The volunteer will be given a schedule of the dates when blood will be drawn and the amount of blood required each time they are contacted. At any time a donor may decline a blood specimen but choose to remain in the study. In most instances, 20 to 200 mL (4 to 40 teaspoons) will be collected at one visit. Visits for one-time or serial blood donations will take approximately ten minutes each and are performed at the Center for Vaccine

Development (CVD) Outpatient Research Clinic.

Blood Unit Donor (large volume). When large volumes of blood are desired, participants may be directed to the Greenebaum Cancer Center (GCC) Cell Component Therapy (CCT) Lab. Visits for the donation of a unit of blood/large volume (200- 500 mL) will take one hour. As part of the GCC CCT lab's standard operating procedure, a CBC will be performed on the day of donation (prior to donation of a unit of blood) for verification of a hemoglobin 12.5 or greater. If the hemoglobin is less than 12.5, the volunteer will be deferred and re-screened at a later date or they may have a smaller volume blood draw (\leq 200 mL) performed at the CVD Outpatient Research Clinic, if eligible by the hemoglobin criteria in *Appendix C*. Additional blood draws will take place according to the schedules attached.

Planned repeat screening labs. The screening blood tests (except for blood typing) will be repeated prior to each scheduled blood donation (small or large volume), but not more often than every 56 days. This is primarily to ensure that the participant is not significantly anemic, but also assesses for any interval abnormality in blood tests since the study duration may be over the course of 8 years.

3.3 Potential Risks

CVD 103-HgR Vaccination

The live oral cholera vaccine, known as Vaxchora (composed of strain CVD 103-HgR), was licensed by the U.S. FDA on June 10, 2016. The adverse reactions to CVD 103-HgR vaccine are generally mild and may include tiredness (30%), headache (28%), abdominal pain (18%), nausea/vomiting (17%), lack of appetite (16%), and diarrhea (4%). The safety and immunogenicity of the live oral cholera vaccine has not been fully established in children (age <18 years), pregnant women, or immunocompromised patients. However, a phase 2 study of the immune response to CVD 103-HgR was performed in HIV patients.²

Risk with Venipuncture

Venipuncture is associated with temporary local pain, some bruising, light-headedness or fainting, and a risk for infection. Infection risk is minimized by the use of alcohol swabs and sterile equipment. Blood will be drawn by trained personnel using clean technique. Volunteers who are found to experience lightheadedness will lie down during and after they have their blood drawn.

Risk of Anemia

Because serial blood draws will be performed in this protocol, there is a risk of anemia. The volumes of blood drawn from each volunteer will be limited to 550 mL every 56 days, and the hematocrit will be checked at regular intervals. Participants found to be anemic will have their scheduled blood draws postponed, be advised to increase iron intake, and have a hematocrit repeated and in the normal range in order to be eligible for the blood draw.

Risk of Loss of Confidentiality

There is always the risk for loss of confidentiality when participants are sharing their personal information. As a standard procedure for all clinical studies, access to clinical information will be limited to the IRB-approved clinical investigators, study coordinator, and research staff. Paper source documents and Case Report Forms (CRFs) will be stored in limited-access rooms and

locked file cabinets. Electronic CRFs will be password protected in a limited access database. IRB-approved research staff will be the only individuals with access to the personal identifiable information and personal health information of research participants.

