4.2 Inclusion Criteria

Volunteers must meet all inclusion criteria in order to be eligible to participate.

1. Age 18 years to 64 years at the time of enrollment
2. Good general health as determined by a screening evaluation within 28 days before blood donation or vaccination
3. Provides written informed consent prior to initiation of any study procedures

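### As written, the 550 mL per 56 days limit covers study draws only: blood given elsewhere is neither asked about nor counted, and Appendix B leaves at most 34.5 mL by Day 29

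*Combined protocol and SAP*

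**What the plan says.** The limit appears in five places in the combined protocol and SAP, each time about blood this study takes.

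- Section 3 says the investigators "have set limits on the total volume of blood to be collected over any 56 day period".
- Section 3.2, for serial donors, allows no more than 2⅓ "cups (550 ml) will be taken over a 2-month period of time".
- Section 3.3, under the risk of anemia: "The volumes of blood drawn from each volunteer will be limited to 550 mL every 56 days".
- Footnote 3 of Appendix A and footnote 3 of Appendix B repeat 550 mL in 56 days and add that schedules vary between volunteers.

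The other protections against anemia act on measured values.

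- Section 3.2: screening labs "will be repeated prior to each scheduled blood donation (small or large volume), but not more often than every 56 days". Unit donors also have a same-day CBC before donation.
- Section 3.3: "Participants found to be anemic will have their scheduled blood draws postponed".
- Section 4.3 and Appendix C exclude low hemoglobin, and section 4.3 excludes anemia treatment in the past 6 months.

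At entry, section 3.1 says "a medical history, concomitant medications, and vital signs are collected". Section 4.2 requires "Good general health as determined by a screening evaluation within 28 days before blood donation or vaccination". Both appendices list an interim history at every visit from Day 1. Sections 3.1 and 4.2 to 4.5 do not mention blood given to a blood bank or another study.

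**The concern.** The protocol guards against anemia in two ways: a ceiling on volume and a check on hemoglobin or hematocrit. The ceiling is useful because it acts before hemoglobin falls, but as written it does not see blood lost outside the study.

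That would matter little if the study used a small part of the allowance. The typical large-volume schedule uses nearly all of it in the first four weeks after vaccination, when hemoglobin checks are sparse. Someone who also gave blood elsewhere in that period could lose well over 550 mL while volunteer and staff both followed the protocol. Participation can last 8 years, with up to 20 draws a year for serial donors, so the question recurs after entry.

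**Working it through.** **Plan's own figure.** The 550 mL is a chosen limit, so there is no derivation to reproduce. Its kitchen equivalent agrees: 2⅓ cups × 236.588 mL = 552 mL.

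**Inputs from Appendix B, as extracted.** PBMC: 150, 150, 100 and 100 mL on Days 1, 3, 8 and 29. CBC 4 mL, serum 8.5 mL and gene expression 3 mL, each printed once in this period, on Day 1. Screening: 15 mL at Visit 1 (Day -28 to -7).

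**Assumed input.** An outside donation of 200 to 500 mL. The range is borrowed from section 3.2, which gives it for the "donation of a unit of blood/large volume (200- 500 mL") visit.

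| Day | Study draw (mL) | Running total | With 200 mL outside | With 500 mL outside |
|---|---|---|---|---|
| 1 | 150 + 4 + 8.5 + 3 = 165.5 | 165.5 | 365.5 | 665.5 |
| 3 | 150 | 315.5 | 515.5 | 815.5 |
| 8 | 100 | 415.5 | 615.5 | 915.5 |
| 29 | 100 | 515.5 | 715.5 | 1,015.5 |

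Room left by Day 29 is 550 − 515.5 = 34.5 mL. Combined loss passes 550 mL on Day 8 after a 200 mL donation and on Day 1 after a 500 mL one.

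**What counts as shortly before Day 1.** Day 29 is 28 days after Day 1. A donation k days before Day 1 is k + 28 days before Day 29, so it shares the 56-day window if k is under 28.

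**Other readings of the table.**

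- Adding the 15 mL screen: 530.5 mL, room 19.5.
- A CBC at every PBMC draw, as footnote 2 describes: 515.5 + 3 × 4 = 527.5 mL, room 22.5. With the screen: 542.5 mL, room 7.5.

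Each reading shrinks the room, so 34.5 mL is an upper bound.

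**Would a hemoglobin check catch it in Days 1 to 29?**

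- Repeat screening is limited to once in 56 days, and Appendix B prints it next at Day 91. From Visit 1 to Day 29 is 29 + 7 = 36 to 29 + 28 = 57 days (one less if there is no Day 0), so a repeat could be due before Day 29 only if Visit 1 was at the very start of its range.
- The same-day CBC belongs to unit donation of 200 to 500 mL. The draws here are 100 to 165.5 mL, within the small-volume class of section 3.
- The footnote 2 CBC is taken with the PBMC draw, for back-calculating lymphocyte subsets. Nothing requires its result before that draw.

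A donation made after Visit 1 could therefore pass unseen unless the volunteer mentions it.

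**Appendix A.** Several visit days were lost in extraction, so the 56-day use of serial donors cannot be computed.

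**The case against.** **The question may already be asked.** Consent pages and the screening and interim history forms were not supplied. Nor were the clinic's SOPs or those of the cell therapy laboratory that takes unit donations. A donation question could sit in any of them. This stands: the point concerns the supplied text and does not show that nobody asks.

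**The 550 mL is a limit on study draws.** Section 3.3 ties the risk to draws made under this protocol, and nothing presents 550 mL as a ceiling on total loss. This also stands. A reader might infer that an outside donation breaches the limit; as worded, it does not. What remains is that the stated reason for the limit, anemia, applies equally to blood lost elsewhere.

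**Hemoglobin falls whatever the source of loss.** The protocol acts on measured values, a Day 1 CBC may in practice be read before Day 3 or Day 8, and exclusion 7 allows investigator judgment. This stands in part. None of these has to produce a result before the early draws, and none counts volume.

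**The schedule is only typical.** True. A reader might also infer that Appendix B itself exceeds the limit: if all 15.5 mL of small tubes recurred at all four visits, the total would be 500 + 4 × 15.5 = 562 mL, or 577 mL with screening. The extracted table cannot show which cells recur, and footnote 3 keeps the limit in force, so the documents do not support that inference.

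**Conclusion.** A cheap safety improvement of minor weight. The supplied text limits study draws only and provides no question or tally for blood given elsewhere. On the typical Appendix B schedule, a volunteer who gave 200 to 500 mL elsewhere shortly before Day 1 could lose about 715 to 1,015 mL in 56 days with every study rule followed.

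This rests on Appendix B as extracted (515.5 mL is a minimum), on the assumed donation size, and on the unsupplied forms and SOPs not covering the matter already.

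The documents do not say how often volunteers give blood elsewhere or how many follow Appendix B, so neither a count of people affected nor an anemia rate can be given. A reader might see an error in the two-month wording of section 3.2. Two months is slightly stricter than 56 days and causes no breach, so it can stay. The statistical analysis is unaffected.

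**What to change.** 1. In sections 3.2 and 3.3, add: *Blood given outside the study in the preceding 56 days counts toward the 550 mL.*
2. Ask the date and approximate volume of any such donation in the screening history and at each interim history, before the draw.
3. Reduce or postpone a draw that would take the combined total above 550 mL.
4. If the donation is found before vaccination, delay Day 1 so that the early samples are kept. On the printed volumes, a 200 mL donation must have left the window by Day 8, so Day 1 should fall at least 56 − 7 = 49 days after it. A 500 mL donation must have left by Day 1, so the wait is 56 days.
5. State an exception to the once-in-56-days rule for screening labs in section 3.2. A Day 1 more than 28 days after Visit 1 needs a new screening evaluation under section 4.2, and the two rules would otherwise conflict.

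**Cost.** One sentence in two places, one question at existing contacts, a few delayed vaccinations and 15 mL for each re-screen. For a donation disclosed after vaccination, a time-critical sample such as Day 3 or Day 8 may be reduced or lost. If existing forms already ask the question, item 2 falls away; the counting rule, what follows from it and the screening exception still need to be written down.

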Appendix C. Clinical Laboratory values, for study eligibility

Parameter	Values Leading to Study Exclusion	
	Low Outlier (or Change from Reference)*	High Outlier (or Change from Reference)*
ALT (SGPT)	N/A	> 1.5 x ULN
AST (SGOT)	N/A	> 1.5 x ULN
WBC [†]	< 0.81 x LLN	> 1.09 x ULN
Hemoglobin [†]	M: < 0.92 x LLN F: < 0.91 x LLN	M: > 1.18 x ULN F: > 1.18 x ULN
Platelet (x 10 ³) [†]	< 0.8 x LLN	> 1.2 x ULN
HIV	Positive	
Blood Type [§]	Not evaluated for eligibility (this test does not need to be repeated)	
For blood unit donations, the following lab values are exclusionary: [‡]		
WBC	<3.5 x10 ³ /mm ³	>11 x10 ³ /mm ³
Hemoglobin	<12.5 g/dL	>18 g/dL
Platelet Count	<150 x10 ³ /mm ³	>500 x10 ³ /mm ³

ULN = Upper limit of normal range

LLN = lower limit of normal range

N/A = not applicable

* Values that lead to exclusion are defined as either an absolute value based on the reference range provided by Garcia (the usual clinical laboratory used by CVD) or the deviation from the reference value of a particular clinical laboratory by the order of magnitude specified. "N/A" means that any lower value is acceptable for inclusion

† Note that different WBC, Hemoglobin, and Platelet Count criteria are defined, for those being evaluated for blood unit (large volume) blood donations

§ Blood Type is performed only once, at initial screening only

[figure not shown]
‡ to be performed by the Cell Component Therapy Facility at University of Maryland Greenebaum Cancer Center, as part of their standard operating procedures

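### Section 3.3 and Appendix C use different measures and limits to decide whether an anemic volunteer may be bled again, and the protocol does not say which governs

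*Combined protocol and SAP*

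**What the plan says.** Section 3.3 (Risk of Anemia) sets a trigger and a return condition. The trigger is: "Participants found to be anemic will have their scheduled blood draws postponed". The return condition is that the volunteer "have a hematocrit repeated and in the normal range in order to be eligible for the blood draw". It gives no number for either and does not refer to Appendix C.

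Section 3.2 (Blood Unit Donor) covers a volunteer whose hemoglobin is below 12.5 on the day of a unit donation: "the volunteer will be deferred and re-screened at a later date or they may have a smaller volume blood draw". The smaller draw, of at most 200 mL, is "performed at the CVD Outpatient Research Clinic, if eligible by the hemoglobin criteria in" Appendix C.

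For draws other than unit donations, Appendix C gives the low hemoglobin limits that exclude as "M: < 0.92 x LLN F: < 0.91 x LLN". Exclusion criterion 4 in Section 4.3 repeats these multipliers.

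Section 3.2 also repeats the screening labs before scheduled donations, at most once every 56 days, and gives the reason: "This is primarily to ensure that the participant is not significantly anemic". That degree of anemia is not defined either. Section 3.1 orders the CBC "to assess total white blood count (WBC), hemoglobin, and platelet count". Hematocrit is not named there and has no limit in Appendix C.

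**The concern.** The two places do not ask the same question. Section 3.3 asks whether the hematocrit is back in the normal range. Section 3.2 and Appendix C ask whether hemoglobin is above a limit set 8% or 9% below the lower end of normal. A volunteer can pass the second test and fail the first.

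At stake is the safeguard against the risk that Section 3.2 gives as the main reason for repeating the labs. Volunteers may be drawn 1 to 20 times a year, under a cap of 550 mL per 56 days, with up to 8 years of planned follow-up. Staff working from Appendix C could bleed a volunteer whom Section 3.3 bars; staff working from Section 3.3 would postpone the same volunteer. The choice also affects which post-vaccination samples are collected.

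**Working it through.** The plan states no figure to reproduce. The check sets the rules side by side and measures the gap between them.

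**Inputs**
- Section 3.3: postponed if anemic (undefined); eligible again when a repeat hematocrit is normal, so not below 1.00 times its lower limit.
- Appendix C, draws other than unit donations: excluded if hemoglobin is below 0.91 × LLN (women) or 0.92 × LLN (men).
- Section 3.2: the smaller-draw alternative opens when hemoglobin is below 12.5 and then applies the Appendix C hemoglobin criteria.
- LLN: not given. Appendix C refers to the clinical laboratory's reference range. The values below are assumptions.

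**Step 1. Hemoglobin below normal but not excluded by Appendix C**
- Women: 0.91 × LLN up to LLN; width (1 − 0.91) × LLN = 0.09 × LLN.
- Men: 0.92 × LLN up to LLN; width (1 − 0.92) × LLN = 0.08 × LLN.

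Both widths are positive for any LLN, so the band always exists.

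**Step 2. Apply both rules in the band, under each reading of anemic**

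| Reading | Volunteer | Section 3.3 | Appendix C |
|---|---|---|---|
| Anemic = below normal | Hemoglobin in the band, hematocrit also low | Postponed until hematocrit is normal | Not excluded |
| Anemic = failing Appendix C | Failed earlier, now recovered to, say, 0.95 × LLN, hematocrit still low | Still barred | Not excluded, since 0.95 exceeds 0.91 and 0.92 |
| Anemic = failing Appendix C | In the band, never failed | Not triggered | Not excluded |

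The rules diverge in the first two rows and agree in the third. Both divergences need a low hematocrit; if the repeat hematocrit is normal, Section 3.3 releases the volunteer.

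**Step 3. Illustration in g/dL, and the part reached by the Section 3.2 route (hemoglobin below 12.5)**

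| Sex | Assumed LLN | Lower edge | Band width | Part of band below 12.5 |
|---|---|---|---|---|
| Women | 11.0 | 0.91 × 11.0 = 10.01 | 0.99 | all |
| Women | 12.0 | 0.91 × 12.0 = 10.92 | 1.08 | all |
| Women | 12.5 | 0.91 × 12.5 = 11.375 | 1.125 | all |
| Men | 12.5 | 0.92 × 12.5 = 11.50 | 1.00 | all |
| Men | 13.0 | 0.92 × 13.0 = 11.96 | 1.04 | 12.5 − 11.96 = 0.54 |
| Men | 13.5 | 0.92 × 13.5 = 12.42 | 1.08 | 12.5 − 12.42 = 0.08 |
| Men | 14.0 | 0.92 × 14.0 = 12.88 | 1.12 | none |

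For women, the Section 3.2 route covers the whole band at each assumed LLN. For men, it depends on the LLN: at 13.5 almost all of the band, and at 14.0 all of it, rests on Appendix C alone.

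**Step 4. Does Appendix C apply after enrollment?** Section 3.2 applies it expressly to the smaller draw. For other small draws this is an inference, but a reasonable one: the labs are repeated before scheduled donations, the schedule footnotes require the results to be reviewed before the draw, and Appendix C exempts only blood type from repetition.

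**The case against.** The strongest case against is that this is an undefined word and not two opposed rules. The only stated low-hemoglobin limits for small draws are in Appendix C, and Section 3.2 speaks of significant anemia. If anemic means failing those limits, a volunteer at 0.95 × LLN who never failed them is not postponed, and no conflict arises at first testing. A stricter condition for return than for first exclusion can be deliberate. Appendix C lists values that exclude and does not oblige anyone to draw from those who pass; Section 3.2 only permits the smaller draw. Both rules could be applied together, with the stricter prevailing.

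Much of this stands. A reader might infer that every volunteer in the band is at once postponed and eligible. The documents do not support that: it requires anemic to mean below normal and the hematocrit to be low as well. A reader might also treat a hemoglobin below 12.5 as below normal; it is a unit-donation cut-off, and the point rests on the LLN multipliers. Nor do the figures show how many volunteers are affected. The 550 mL limit is a cap, draws become less frequent after the first year, and repeat labs and withdrawal for abnormal results or well-being remain.

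What does not stand is that the text settles the matter. Nothing says that the stricter rule prevails, that Section 3.3 is a deliberately higher bar for return, or that anemic means failing Appendix C. Section 3.3 also turns on a measure for which the eligibility table has no limit.

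**Conclusion.** The point holds as an unresolved relation between two eligibility rules. On either natural reading of anemic, some volunteers are barred by Section 3.3 and not excluded by Appendix C: those in the band at testing on one reading, those who recover into it on the other. The gap is 9% of the LLN for women and 8% for men, about 1.0 to 1.1 g/dL at the assumed LLNs. It matters only where the hematocrit is also below normal.

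The multipliers, the differing measures, the missing definition and the missing order of precedence come from the documents. The g/dL values are illustrations, and the use of Appendix C outside the Section 3.2 route is partly inferred. The issue is volunteer safety and consistent sample collection; no endpoint definition, planned test or sample-size statement changes. It should be corrected, but it does not show that protection against anemia is absent.

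**What to change.** Reconcile Sections 3.2 and 3.3 and Appendix C as follows:

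- Define anemic for repeat draws, and say whether the significant anemia mentioned with the repeat labs in Section 3.2 is the same thing.
- Name the measure that decides, hemoglobin or hematocrit, and give its limit where staff look up eligibility.
- State how the Section 3.3 return condition relates to the Appendix C limits, and which governs when they differ. Separate limits for first exclusion and for return may remain if the text says so.
- Put cross-references in all three places.

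The investigators and the safety monitor should set the values; none is proposed here. The cost is protocol wording, with the IRB approval that Section 9.2 requires for any amendment. No extra blood test is needed, since a CBC is already among the repeat labs.
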